3.1 Study Population

We aim to enroll 20 neonates born under 32 weeks of gestational age at the Royal Hospital for Children in Glasgow. Neonates will be enrolled during the first 3 days of life with written informed consent signed by their parents.

3.2 Inclusion criteria

- Male preterm infants born ≤ 32 weeks of gestational age
- Written informed consent provided

3.3 Exclusion criteria

- Female sex assignment at birth
- Male preterm infants born > 32 weeks of gestational age
- Male infants born at term

3.4 Identification of participants and consent

The family of a newborn eligible for this study will be approached in the neonatal unit after the birth. Information material about the study shall be provided with an initial private discussion and we will make the family aware that participation is voluntary and they can leave the study at any time without their baby's standard care being affected. We will ask for contact details during this first meeting in order to contact them later checking whether they are interested in participating and start with the study. Consent will be taken in the Neonatal Intensive Care Unit in a private counselling room by the research team ([name] or [name] or [name]). Parents will be given a minimum of 24 hours to consider participation and they could take a decision until 72 hours of newborn's life. Neonates of parents who will provide written informed consent will be enrolled in this study.

3.5 Withdrawal of subjects

Participants have the right to withdraw from the study at any point for any reason.

4 Study Outcome Measures

Our study will include 3 types of different evaluations on each neonate:

- Multiple urine collections to evaluate urinary gonadotrophin levels
- Multiple clinical evaluations of auxological parameters and external genitalia
- Neurocognitive assessment at 3 months of corrected gestational age

Timing of sample analysis and simultaneously clinical evaluation will be as follow:

T1: 1-3 days of life

T2: 7 days of life

T2a – T2z: one per week until 40 weeks of post-conceptual age or until discharge from Neonatal Unit

T3-TX: urinary sample analysis and clinical evaluation during the routine follow up clinics until 12 months of corrected gestational age

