A second post-natal HPG activation, also called "minipuberty", occurs at around 1 week of age, when placental hormones are cleared from the circulation. From the first weeks of life onwards there is a progressive increase in gonadotropins levels with a greater increase of FSH in females and of LH in males. During the "minipuberty" period gonadotropins levels have a peak at 3 months of life and a progressive exhaustion at around 6 months, except for FSH levels in females that can remain high even up to 3 or 4 years. Particularly in males, testosterone and androgen levels are associated with development and maturation of the reproductive system (penis and testis) as well as the androgynous cutaneous manifestations and a different neurobehavioral structure.⁵ Postnatal testosterone levels have been associated with male-type behaviour in 14-month-old infants, suggesting a role in neurobehavioral development.⁶ Recently, it has also been suggested how the increasing testosterone level during the first 6 months of life, as well as during puberty, translates into an increase of linear growth, regardless of the levels of growth hormone (GH) or insulin-like growth factor (IGF1).⁷ Preterm birth does not seem to influence post-natal HPG activation, since that gonadotropin levels seem to raise up at the same time as term infants after the birth. The difference is that in preterm neonates these values last higher and longer than full-term newborns. According to the most recent longitudinal data, the post-natal activity of this axis declines at about the same in term neonates compared to premature infants with the same corrected gestational age, suggesting that the HPG activity is evolutionarily regulated.^{8,9} This higher increase of gonadotropin levels in premature males has been associated with a faster penile and testicular growth after birth compared to full-term boys. At last, in neonates small for gestational age (SGA) there are some evidence that post-natal FSH and testosterone levels are higher compared to infants with an adequate weight (AGA), although it is not known

whether this correlates or have any influence on the catch-up growth of this subjects.^{10,11} Understanding how “minipuberty” can influence linear growth, genitalia development and neurocognitive processes in preterm neonates has a significant scientific impact and could provide us more information in understanding auxological and neurobehavioral developmental patterns of this population.

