2. Aim/Primary and Secondary Objectives

This is a preliminary prospective and crosssectional study aiming to describe “minipuberty” in male preterm children at the Royal Hospital for Children in Glasgow. The research project has been discussed by the Developmental Endocrinology Research Group at the University of Glasgow.

- **Primary Endpoint**

- To describe when urinary hormones (follicle stimulating hormone and luteinising hormone) start to raise and when they reach their peak among male preterm neonates born with a gestational age <32 weeks.
- To investigate if there is a difference in hormone levels and their peak timing between extremely preterm babies (<28 weeks of gestational age) and very preterm babies (28-32 weeks of gestational age).

- **Secondary endpoints**

- Identify a link between hormone levels and linear growth in the first months of life in preterm neonates.
- Identify a link between hormone levels and the development of external genitalia (testicular volume and position, penile length).
- Identify a link between hormone levels and short-term neurocognitive development.

3. Study Design

This is a preliminary prospective and cross-sectional study on male preterm children at the Royal Hospital for Children in Glasgow. The study will not include any investigational medical product. The research project has been discussed by the Developmental Endocrinology Research Group at the University of Glasgow.

This study will be performed according to the Research Governance Framework for Health and Community Care (Second edition, 2006).

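### Weekly urine sampling starts on postnatal age but stops at 40 weeks post-conceptual age or discharge, so comparing observed peak times between gestational-age groups can reflect the schedule; peak, onset, level and age scale are undefined

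*Combined protocol and SAP*

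**What the plan says.** Section 2 makes two things primary. The first is to describe when urinary FSH and LH "start to raise and when they reach their peak". The second is "To investigate if there is a difference in hormone levels and their peak timing between extremely preterm babies" (below 28 weeks) and very preterm babies (28–32 weeks).

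Section 4 sets the schedule. T1 is at days 1–3 and T2 at day 7 of life. Samples are then "one per week until 40 weeks of post-conceptual age or until discharge from Neonatal Unit". After that, urine is taken at routine follow-up clinics to 12 months corrected age, with no clinic ages given. The schedule thus uses three clocks: days of life, post-conceptual age and corrected age.

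Section 1 says that activation "occurs at around 1 week of age" and that "gonadotropins levels have a peak at 3 months of life". For the decline it turns to corrected age: postnatal activity "declines at about the same in term neonates compared to premature infants with the same corrected gestational age".

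Section 6 names the Mann-Whitney U test for nonparametric comparisons, with p < 0.05. Neither it nor Section 4.1 defines onset, peak, the level to be compared or the age scale, or says how unequal sampling periods are handled.

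Eligibility is worded in two ways. Section 3.1: "We aim to enroll 20 neonates born under 32 weeks of gestational age". Section 3.2: "Male preterm infants born ≤ 32 weeks of gestational age".

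**The concern.** The two groups are defined by gestational age, and gestational age also decides how long each infant is sampled weekly. An infant born earlier has more weekly samples, and later ones on the postnatal scale, than an infant born near 32 weeks. A maximum can only be found where there is a sample. If the hormone peak falls after one group's weekly sampling has ended but within the other's, the observed peak time and height can differ even when the true curves are the same, or a true difference can be hidden.

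The choice of age scale adds to this. A peak tied to post-conceptual age comes later after birth in the more preterm group, so the answer to a primary question can change with a scale that the plan does not name.

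**Working it through.** The plan gives no calculation on this point, so there is no figure to reproduce.

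**Step 1. Last weekly sample.** Inputs: weekly samples from day 7 and a stop at 40 weeks (280 days), from Section 4. I take post-conceptual age as gestational age at birth plus postnatal age. Formula: last week = whole part of (280 − gestational age in days) / 7.

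| Birth | Days | 280 − days | Last weekly sample |
|---|---|---|---|
| 24+0 | 168 | 112 | week 16 |
| 26+0 | 182 | 98 | week 14 |
| 27+0 | 189 | 91 | week 13 |
| 27+6 | 195 | 85 | week 12 |
| 28+0 | 196 | 84 | week 12 |
| 31+6 | 223 | 57 | week 8 |
| 32+0 | 224 | 56 | week 8 |
| 32+6 | 230 | 50 | week 7 |

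All infants share postnatal weeks 1–8, or weeks 1–7 if 32+6 is eligible.

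**Step 2. Set this against the plan's own peak age.** Three months is 3 × 52/12 = 13.0 weeks. Infants born at 26+0 or earlier have weekly samples on both sides of week 13. For births at 26+1 to 27+0, week 13 is the last weekly sample. From 27+1 onwards, and so for every infant in the 28–32 week group, it lies beyond the weekly samples.

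**Step 3. Discharge.** If discharge comes first, the last week for an infant born at 31+6 is (259 − 223)/7 → 5 at 37 weeks, (252 − 223)/7 → 4 at 36 weeks and (245 − 223)/7 → 3 at 35 weeks. These discharge ages are assumed.

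**Step 4. False positives for peak time.** Simulation with no true group difference. Everything here is assumed: 10 v 10 infants; gestational age uniform over 24+0 to 27+6 and 28+0 to 31+6; clinics at 3, 6, 9 and 12 months corrected, with or without one at 6 weeks corrected. Log level is a Gaussian curve in postnatal age (SD 4 or 8 weeks, height 1 or 2, between-infant SD of peak age 0 or 2 weeks), plus infant SD 0.4 and within-infant SD 0.3 or 0.5. That makes 16 settings. Each infant's date of maximum is compared by two-sided Mann-Whitney at 0.05.

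| True peak, end of weekly sampling | Range over settings |
|---|---|
| Week 6, 40 weeks | 3–8% |
| Week 8, 40 weeks | 4–15% |
| Week 13, 40 weeks, clinic at 6 weeks corrected | 6–16% (median 8) |
| Week 13, 40 weeks, no clinic before 3 months corrected | 30–100% (median 65) |
| Week 6, discharge at 37 weeks | 12–25% |
| Week 8, discharge at 37 weeks | 22–86% |

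Repeat runs moved these limits by a few points. Restricted to the shared weeks, the same test gave 3–7%.

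The direction is not fixed. With a week-13 peak, a 40-week stop and no early clinic, the group below 28 weeks looked about 3 weeks later. With discharge at 36 weeks and a clinic at 6 weeks corrected, it looked about 6 weeks earlier.

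**Step 5. Peak level.** The result turns on between-infant SD, which the documents do not give. For the week-13, no-early-clinic case, median false positives for level were about 61% at SD 0, 28% at 0.4, 10% at 0.8 and 8% at 1.2. Peak-time medians stayed at 64–70% over the same SDs.

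**Step 6. Age scale.** With every infant's peak set at 38 weeks post-conceptual age and no between-infant variation, the groups differed by about 4 weeks on postnatal age (significant in 96–100% of runs) and by 0 on post-conceptual age (3.5–5.0%).

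**The case against.** Several points on the other side are fair.

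- **The biased analysis is not written down.** This stands. The plan names a test, not a variable, so the bias depends on how the gap is filled. Week-by-week comparison would avoid it, but means about eight tests per hormone; with no true difference, at least one reached p < 0.05 in 16–28% of simulated runs.
- **A 40-week stop is reasonable.** This stands. It suits an analysis on post-conceptual age, and Section 1 places the decline on corrected age. A reader might infer that the stop is a design error; the documents do not support that.
- **Sampling continues after the stop.** True: only the weekly phase ends. But the clinic ages are not given, and whether one falls near 6 weeks corrected moves the week-13 median from 8% to 65%.
- **The 3-month peak is a general figure.** This stands. Section 1 does not give it for preterm infants. With peaks at weeks 6–8 and a 40-week stop the distortion is small or modest.
- **The study is preliminary, with 20 infants and a descriptive first objective.** True, but the group comparison is listed as primary and carries a significance threshold.

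**Conclusion.** The point holds as a gap in the plan with a material possible consequence. That weekly sampling length depends on gestational age is certain under the 40-week rule. That peak timing will be wrongly reported is not certain: it requires comparison of observed maxima, and the size depends on peak age, discharge age and clinic ages, none of which the documents fix for these infants. Under the stated assumptions, false positives for peak time are about 30–100% for a week-13 peak with no clinic before 3 months corrected, about 5–18% with a clinic at 6 weeks corrected, and near nominal up to about 15–20% for peaks at weeks 6–8 with a 40-week stop. Earlier discharge raises the figures for these early peaks.

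Three stronger readings go too far. One is that the plan will show the more preterm group peaking later and higher; the direction can reverse. Another is that level is biased by a known amount; no single level or power figure should be relied on. The third is that onset is distorted by the stop rule; Section 1 puts activation at about 1 week, where both groups have the same schedule, so onset is undefined rather than biased.

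This should be fixed; confidence is medium.

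**What to change.** Settle the following before hormone results are seen.

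1. **Age scale.** Name one primary scale, for example postnatal age, and report the other as supportive. A window shared on one scale does not protect the comparison on the other.
2. **Level.** Do not test raw maxima between groups. Compare mean log LH and mean log FSH by Mann-Whitney over a window fixed in advance: for example postnatal weeks 1–8 if weekly sampling runs to 40 weeks and gestational age is below 32+0, or a named shorter window if earlier discharge is expected. Use each infant's available samples with a stated minimum number. Say how discharge, withdrawal and missed samples are handled, so that the shortest-followed infant does not set the window afterwards. State that this tests early level, not peak height. A longitudinal model of all samples on the chosen scale is an acceptable alternative or supportive analysis.
3. **Peak time.** Report it as the interval between neighbouring samples. Mark it unresolved if the maximum is at or after the last weekly sample, and give the number unresolved by group. Keep timing descriptive unless most peaks in both groups fall inside the shared window.
4. **Onset.** Define it, with a fallback reference sample such as T2. Section 3.4 gives parents at least 24 hours and up to 72 hours of life to decide, so T1 may be missing.
5. **Consistency.** State the ages of the clinic samples and reconcile the two eligibility wordings.

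This is a cheap improvement: protocol and analysis-plan wording and a small analysis, with no added infants, visits or samples. The downsides are real. The shared window tests early level only and has little power for timing. A late peak may stay unresolved. The window shortens to about week 3–5 if infants are discharged at 35–37 weeks. Power for level depends on the unknown between-infant SD: a two-fold difference present at all ages was detected in 65–96% of simulated runs at SD 0.4, but 14–25% at 1.2. The different urine collection method below 28 weeks (Section 4.1) also remains as a separate explanation for a group difference.

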4.1 Primary Outcome Measure

Urine collection will be done with a plastic bag with a sticky strip on one end, made to fit over baby's genital area. In extremely preterm babies (<28 weeks of gestational age) urine collection will be from cotton wool in the nappy because of their sensitive skin.

Samples will be analyzed on fresh urine for urinary gonadotropin levels (FSH, LH) as detailed in laboratory tests section.

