Primary Objective:	
 - To describe when urinary hormones (follicle stimulating hormone and luteinising hormone) start to raise and when they reach their peak among male preterm neonates born with a gestational age <32 weeks. - To investigate if there is a difference in hormone levels and their peak timing between extremely preterm babies (<28 weeks of gestational age) and very preterm babies (28-32 weeks of gestational age).
Secondary Objective:	
 - Identify a link between hormone levels and linear growth in the first months of life in preterm neonates. - Identify a link between hormone levels and the development of external genitalia (testicular volume and position, penile length). - Identify a link between hormone levels and short-term neurocognitive development.
Rationale:	The knowledge about the activation of the hypothalamic-pituitary-gonadal axis (HPG) in the first months of life is relatively recent. It is scientifically proven that in this period, called "minipuberty", there is the same activation that occurs during puberty. This is responsible for changes in terms of growth, pubertal development and neurobehavioral patterns. Understanding all the factors involved in children's physical and neurocognitive development has a significant scientific impact and could provide useful information in case of future problems. As prematurity survival rates continue to improve, clinicians need to be familiar with the hormonal changes in these patients and the first months of life provide a 'window of opportunity' for functional studies of the HPG axis prior to pubertal development
Methodology:	This is a preliminary prospective and cross-sectional study.
Sample Size:	20 male preterm neonates with a gestational age ≤ 32 weeks
Main Inclusion Criteria:	
 • Male preterm infants born ≤ 32 weeks of gestational age • Written informed consent provided
Main Exclusion Criteria:	
 • Female sex assignment at birth • Male preterm infants born >32 weeks of gestational age • Male infants born at term

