4.3 Laboratory Tests

Measurement of LH and FSH urinary levels will be made on fresh samples using electro-chemiluminescence immunoassay (ECLIA). Sample analysis will be performed by the Biochemistry Department of the Royal Hospital for Children in Glasgow using Abbott Architect i1600 instrument.

5. Assessment of Safety

We do not expect particular problems in this study. Urine collection will be made in the same way of routine collection in infants. Auxological evaluations are part of the routine care of preterm neonates and we will add a non-invasive evaluation of external genitalia without particular risks for the babies. Neurobehavioural development will be evaluated using parents' video only if they agree with video recording their baby. This will allow parents to stay at home without bringing their baby to the hospital.

6. Statistics and Data Analysis

Results shall be expressed as median (range) and analysed using Minitab. Some data may require log transformation. Pearson's correlation shall be used for univariate analysis of association of and multivariate analysis shall be performed using backward stepwise linear regression analysis including factors significant from univariate analysis (Pearson's correlation) as independent factors. The Mann Whitney U test shall be used for comparison of nonparametric data. Statistical significance shall be set at $p < 0.05$.

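### Urine collection method changes at the same 28-week boundary as the primary comparison of LH and FSH levels, so any method effect cannot be separated from the gestational-age effect

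*Combined protocol and SAP*

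**What the plan says.** The second primary objective, in the synopsis and again in section 2, is a group comparison. It covers "hormone levels and their peak timing between extremely preterm babies (<28 weeks of gestational age) and very preterm babies (28-32 weeks of gestational age" (LH and FSH in urine).

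Section 4.1 describes a bag with a sticky strip as the way urine is collected, then makes one exception: "In extremely preterm babies (<28 weeks of gestational age) urine collection will be from cotton wool in the nappy because of their sensitive skin".

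Section 4 sets samples at 1-3 days and 7 days, then "one per week until 40 weeks of post-conceptual age or until discharge from Neonatal Unit", then "urinary sample analysis and clinical evaluation during the routine follow up clinics until 12 months of corrected gestational age". Neither section 4 nor 4.1 says whether the exception continues after discharge. Section 4.2 times the genital examination to the placing of the bag and does not repeat the cotton-wool exception. Section 5 says only that urine is collected as it is routinely in infants.

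For the group comparison, section 6 says: "The Mann Whitney U test shall be used for comparison of nonparametric data". It also plans backward stepwise regression on factors significant in univariate analysis. Collection method is not named as a factor. The documents describe no overlap between methods, no paired specimens, no recovery check for cotton wool and no record of the method used for each sample.

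**The concern.** The two groups being compared would have their outcome measured in two different ways, with the change of method falling exactly on the group boundary. If urine recovered from cotton wool reads lower or higher than urine from a bag, that offset adds to whatever real difference exists. A reported difference in LH or FSH could then be a collection effect, and a real difference could be hidden by one. The study would hold no data to tell these apart.

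The levels comparison is half of the second primary objective and is to be tested at p < 0.05, so this bears on a headline result.

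**Working it through.** **Inputs from the documents.** Groups: <28 v 28-32 weeks (section 2). Method: cotton wool v bag, split at <28 weeks (4.1). Total: 20 infants (3.1). Test: Mann-Whitney, significance at 0.05 (section 6), taken as two-sided. The plan gives no power, effect size, SD or group split, so it has no figure of its own to reproduce.

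**Step 1: can method and group be separated?** Let G = 1 for infants born <28 weeks and M = 1 for cotton wool. Under 4.1 as written, M = G for every infant. A model with an intercept, G and M has rank 2 out of 3, whether the split is 10 v 10 or 6 v 14. Only the sum of the two effects can be estimated, so adding method as a covariate would not help.

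**Step 2: effect on the ratio of levels.** Let r be the ratio of the cotton-wool reading to the bag reading for the same urine.

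observed ratio (<28 v 28-32) = true ratio × r

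A loss L gives r = 1 − L. With a true ratio of 1, losses of 10%, 20%, 30% and 40% give observed ratios of 0.9, 0.8, 0.7 and 0.6. A true ratio of 1.43 with r = 0.7 gives 1.43 × 0.7 = 1.0, so a real difference disappears. Evaporation would act the other way, with r > 1. This step needs no SD.

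**Step 3: false-positive rate.** Assumptions not in the documents: one value per infant, normal on the log scale, no true difference. The offset in SD units is −ln(1 − L)/SD. For L = 0.3 it is 0.357/0.5 = 0.71, 0.357/1.0 = 0.36 or 0.357/1.5 = 0.24. Exact two-sided Mann-Whitney at 10 v 10 (reject if the smaller U ≤ 23; test size 4.3%), 200,000 simulated trials per setting:

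| Log SD | L = 10% | 20% | 30% | 40% |
|---|---|---|---|---|
| 0.5 | 6% | 14% | 29% | 53% |
| 1.0 | 5% | 7% | 10% | 17% |
| 1.5 | 5% | 5% | 7% | 10% |

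At 6 v 14 (test size 4.1%), losses of 30% and 40% give about 24% and 44% at log SD 0.5, and 9% and 14% at log SD 1.0. The test is two-sided and the data symmetric on the log scale, so a gain by a factor 1/(1 − L) gives the same rates as a loss L.

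**Step 4: timing.** If an infant's true profile is h(t) and every sample is read as r × h(t), the maximum falls at the same t, so peak timing does not move. A rise judged against the infant's own baseline does not move either. A rise judged against a fixed threshold k could, because r × h(t) > k requires h(t) > k/r. The plan does not define onset.

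**The case against.** The strongest reply is that no bias has been shown. That is correct. A reader might infer that cotton wool lowers LH and FSH and that the comparison is therefore biased. The documents do not support this: they give no recovery figure, and the offset could go either way. Every rate in the table rests on an assumed offset, SD and split, and serious inflation needs a large offset together with a small SD. What stands is the structure: the design cannot estimate the offset, so its absence could not be demonstrated afterwards.

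A second reply is that section 4.1 gives a skin-protection reason and the study is a preliminary one of 20 infants. The reason explains the rule without removing the confounding, and the comparison is still listed as a primary objective with a significance level.

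A third is that infants born <28 weeks may move to a bag later, so that the confounding is not total. Section 4.2, which mentions only the bag, could be read that way, but no section states a change of method. Even if there were one, samples taken before it would remain fully confounded. For the same reason, a reader who infers that a switch would disturb the timing of the peak goes further than the text: no switch is stated, and when the peak occurs in preterm infants is what the study sets out to describe.

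Finally, moving all infants to one method has a cost for the first primary objective. That stands and is set out with the fix.

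**Conclusion.** The concern holds for levels. With collection as written, any method effect is fully confounded with the <28 v 28-32 week comparison of LH and FSH, and nothing in section 6 can separate them. This follows from the text alone and needs no assumption.

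Its practical size is unknown. It ranges from negligible (losses of 10-20% with a log SD of 1.0 or more leave the false-positive rate at about 5-7%) to serious (29-53% for losses of 30-40% with a log SD of 0.5), on the assumptions in step 3.

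A reader might extend the point to both primary objectives. The documents do not support that: within-infant onset and peak timing are largely unaffected if each infant's method stays constant, apart from onset defined by a fixed threshold. Sections 4.1 and 4.2 must be reconciled on which method is used in infants born <28 weeks, and for how long. This should be fixed, at medium confidence, because the confounding is certain and the bias is not.

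**What to change.** Amend section 4.1 so that both groups are sampled at matched time points by one collection method that the clinical team accepts for all infants. Record the method for every sample, state whether and when it may change, and bring section 4.2 into line.

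The cost is an amendment and one extra field per sample, with no extra assays. The downside is that specimens may be smaller, and a common recovery loss could lower absolute levels and delay threshold-based onset in all infants. A common proportional loss would, however, cancel from the between-group ratio and leave peak timing unchanged.

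Only if two methods must stay: report the levels comparison as confounded by collection method. Where specimen volume allows, split some bag specimens from infants born at 28-32 weeks, assay them directly and after cotton-wool extraction, and use the log ratio in a sensitivity analysis. This costs one extra LH and one extra FSH result per split specimen. If the SD of the log ratio is 0.1-0.2 (assumed), the 95% half-width t × SD/√n is 0.072-0.143 for 10 specimens (a factor of 1.07-1.15) and 0.124-0.248 for 5 (1.13-1.28). The report should state that this check covers extraction recovery only. It does not cover time in the nappy, evaporation or contamination, so it does not remove the confounding.
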